CLINICAL STUDY PROTOCOL

X16047
UC IRB# 14-0899

Phase II Randomized Trial of Continuation of Post-Transplant Maintenance with Single-Agent lenalidomide vs. Consolidation/Maintenance with Ixazomib-lenalidomide-Dexamethasone in Patients with Residual Myeloma

Indication: Post-transplant maintenance

Phase: Phase II

Protocol History	
Original	01 JUL 2014
Version 1.1	09 JUN 2015
Version 1.2	10 SEP 2015
Version 2	14 DEC 2015
Version 2.1	4 APR 2016
Version 2.2	26 OCT 2016
Version 2.3	19 JUN 2017
Version 2.4	14 JUN 2019
Version 2.5	17JUL2019
Version 2.6	25Sept2019

Investigator and Coordinating Study Center:

[name] [name]
The University of Chicago
[name]
[name]
[contact]

This is a multi-institution investigator-initiated study. The principal investigator **[name]** (who may also be referred to as the sponsor-investigator) is conducting the study and acting as the sponsor. Therefore, the legal/ethical obligations of the principal investigator include both those of a sponsor and those of an investigator.

PROTOCOL SUMMARY

Study Title: Phase II Randomized Trial of Continuation of Post-Transplant Maintenance with Single-Agent lenalidomide vs. Consolidation/Maintenance with Ixazomib-lenalidomide-Dexamethasone in Patients with Residual Myeloma

Phase: II

Number of Patients: 60

Study Objectives

Primary

- To determine the rate of MRD-negative disease by multiparameter flow cytometry (MFC) for patients enrolled based on MFC-positivity or by next generation sequencing (NGS) for patients enrolled based on NGS-positivity (with MRD-negative disease by MFC at screening), at 12 months after randomization

Secondary

- Evidence of response as demonstrated by the improvement of the depth of response by at least one category according to IMWG response criteria. (For example, an improvement from very good partial response (VGPR) to near complete response (nCR) or better than nCR including conversion from CR to MRD negative disease [overall response]) at 6 and 12 months.
- Estimate of progression free survival
- Estimate of overall survival
- Estimate of duration of MRD-negative disease
- Safety and tolerability of experimental arm vs. control

Tertiary/Exploratory (*if applicable*)

- Determination of markers of response based on pre-treatment characteristics using methods described in correlative research, protocol section 8.
- Evaluation of MRD by gene sequencing method using the Adaptive Biotechnologies platform (clonoSEQ®) in parallel with multi-parameter flow cytometry (MFC)

Overview of Study Design:

This is a phase 2, open-label, randomized study in which subjects are enrolled 1:1 control to experimental arm stratified by 1) level of response at study entry (in accordance with the IMWG uniform response criteria) and 2) risk factors:

- 1) Level of response including transplant; response is assessed at study screening for this protocol:
 - i. <VGPR
 - ii. \geq VGPR
- 2) Risk Factors at the time of diagnosis:
 - i. At least one of the following poor prognostic risk factors (Yes/No):
 1. del-13 (by karyotyping)
 2. hypodiploidy (by karyotyping)
 3. t(4;14) (by FISH)
 4. t(4;16) (by FISH)
 5. t(14;20) (by FISH)
 6. del17p (by FISH)
 7. 1q21 gain (by FISH)

Dose Schedule

Each cycle is 28 days for both the Control arm and Experimental Arm.

Cycle	CONTROL	EXPERIMENTAL		
	Lenalidomide	Lenalidomide	Ixazomib	Dex ^b
Cycle 1 - 4	Last best tolerated dose of either 10 or 15 mg. If the 10 mg dose is tolerated for 3 cycles, either off or on protocol , it can be escalated to 15 mg per dose	25 mg daily	First cycle 3 mg per dose; can be escalated to 4 mg per dose in cycle 2	Initially 40 mg weekly (or last best tolerated dose prior to transplant)
Cycle 5 - 12	Best tolerated dose	Best tolerated dose	Best tolerated dose	STOP*
Treatment Days	1 - 28	1 - 21	1, 8, 15	1, 8, 15, 22

- 1) * A total of 20 mg of dexamethasone weekly or prednisone equivalent will be permitted to improve/prevent toxicities (ex. rash or GI side effects)

Study Population: Post-Transplant Multiple Myeloma on Lenalidomide Maintenance

Key Inclusion Criteria:

- 1) Patients who completed induction treatment followed by autologous stem cell transplant as initial therapy for symptomatic myeloma as per IMWG criteria and are considered for single agent Lenalidomide maintenance or initiated single agent Lenalidomide maintenance
 - a. Patients will be eligible for enrollment in the first 0-6 months of lenalidomide maintenance provided that lenalidomide maintenance has been initiated within 6 months after transplant as per standard of care.
 - i. Patients do not have to be on Lenalidomide at the time of study consent.
 - b. Patients already in lenalidomide must be receiving lenalidomide 10 mg or 15 mg (as per CALGB trial, McCarthy et al., N Eng J Med, 2012) and be able to tolerate dose escalation to 25 mg daily.
 - c. Patients receiving off protocol lenalidomide maintenance cannot exceed 6 months post-transplant
 - d. A one week break from off protocol lenalidomide is suggested, prior to initiating treatment on the study
 - i. Any delays >7 days to align treatment with the start of Cycle 1 Day 1, of either arm, must be discussed with the PI.
 - e. Patients who completed tandem transplantation will be eligible for enrollment
- 2) No evidence of progressive disease on lenalidomide
- 3) Evidence of minimal residual disease at the time of screening defined as at least MRD-positive disease
 - a. A primary method of evaluation of MRD is Multi-parameter Flow Cytometry (MFC) performed at University of Chicago
 - b. Patients who have negative MRD by Multi-Parameter Flow Cytometry (MFC) but have residual original monoclonal protein by serum or urine immunofixation may be eligible if they are found to have MRD-positive disease by Next Generation Sequencing (NGS).
 - c. If patient is receiving lenalidomide, any delays required to align treatment with the start of Cycle 1 of either arm, must be discussed with the PI.
- 4) Bone marrow specimen will be required at study entry; available DNA sample will be used for calibration step for MRD evaluation by gene sequencing
- 5) Males and females ≥ 18 years of age
- 6) Life expectancy of more than 3 months
- 7) ECOG performance status of 0-2
- 8) Adequate hepatic function, with bilirubin $\leq 1.5 \times$ ULN and aspartate aminotransferase (AST) and alanine aminotransferase (ALT) $\leq 3 \times$ ULN
- 9) ANC $\geq 1.0 \times 10^9/L$, hemoglobin $\geq 8 \text{ g/dL}$, platelet count $\geq 75 \times 10^9/L$.
- 10) Calculated creatinine clearance (by Cockcroft-Gault) $\geq 50 \text{ ml/min}$ or serum creatinine below 2 g/dL (section 13.2)
- 11) Voluntary written consent must be given before performance of any study related procedure not part of standard medical care, with the understanding that consent may be withdrawn by the patient at any time without prejudice to future medical care.
- 12) Female patients who:
 - a. Are postmenopausal for at least 1 year before the screening visit, OR
 - b. Are surgically sterile, OR

- c. If they are of childbearing potential, agree to practice 2 effective methods of contraception, at the same time, from the time of signing the informed consent form through 90 days after the last dose of study drug, OR
- d. Agree to practice true abstinence when this is in line with the preferred and usual lifestyle of the subject. (Periodic abstinence [e.g., calendar, ovulation, symptothermal, post-ovulation methods] and withdrawal are not acceptable methods of contraception.)

13) Male patients, even if surgically sterilized (i.e., status post-vasectomy), must agree to one of the following:

- a. Agree to practice effective barrier contraception during the entire study treatment period and through 90 days after the last dose of study drug, OR
- b. Agree to practice true abstinence when this is in line with the preferred and usual lifestyle of the subject. (Periodic abstinence [e.g., calendar, ovulation, symptothermal, post-ovulation methods] and withdrawal are not acceptable methods of contraception.)

Exclusion

[figure not shown]
- 14) Evidence of progressive disease on lenalidomide maintenance as per IMWG criteria
- 15) Patients who have already started or received multi-drug consolidation regimen post-transplant except for patients receiving up to 6 months of single agent lenalidomide maintenance
- 16) Longer than 12 months since the initiation of induction therapy at the of start of lenalidomide maintenance
- 17) Prior progression after initial therapy.
 - a. Subjects, whose therapy changed due to suboptimal response, intolerance, etc., remain eligible, provided they do not meet criteria for progression.
 - b. No more than two regimens will be allowed excluding dexamethasone alone.
- 18) Diarrhea > Grade 1 in the absence of anti-diarrheals
- 19) Central Nervous System involvement
- 20) Female patients who are lactating or have a positive serum pregnancy test during the screening period.
- 21) History of allergy to mannitol
- 22) Major surgery within 14 days before enrollment.
- 23) Radiotherapy within 14 days before randomization. If the involved field is small, 7 days will be considered a sufficient interval between treatment and administration of the ixazomib.
- 24) Evidence of current uncontrolled cardiovascular conditions such as hypertension, cardiac arrhythmias, symptomatic congestive heart failure or New York Heart Association Stage III and IV, or unstable angina, or myocardial infarction within the past 6 months.
- 25) Rate-corrected QT interval of electrocardiograph (QTc) > 470 msec on a 12-lead ECG during screening
- 26) Uncontrolled diabetes
- 27) Acute infection requiring systemic anti-infectives, antivirals, or antifungals within two weeks prior to first dose
- 28) Systemic treatment, within 14 days before the first dose of ixazomib, with strong CYP3A inducers (rifampin, rifapentine, rifabutin, carbamazepine, phenytoin, phenobarbital), or use of Ginkgo biloba or St. John's wort.
- 29) Ongoing or active systemic infection, active hepatitis B or C virus infection, or known human immunodeficiency virus (HIV) positive.
- 30) Any serious medical or psychiatric illness that could, in the investigator's opinion, potentially interfere with the completion of treatment according to this protocol.
- 31) Known allergy to any of the study medications, their analogues, or excipients in the various formulations of any agent.

32) Known GI disease or GI procedure that could interfere with the oral absorption or tolerance of ixazomib including difficulty swallowing.
33) Diagnosed or treated for another malignancy within 2 years before study enrollment or previously diagnosed with another malignancy and have any evidence of residual disease. Patients with non-melanoma skin cancer or carcinoma in situ of any type are not excluded if they have undergone complete resection.
34) Patient has \geq Grade 3 peripheral neuropathy or Grade 2 with pain on clinical examination during the screening period.
35) Participation in other clinical trials, with other investigational agents not included in this trial, within 30 days of the start of this trial and throughout the duration of this trial.

Duration of Study:

Subjects will be treated on protocol for 12 months or until disease progression or if lenalidomide and/or ixazomib are permanently discontinued due to intolerance before the end of 1 year. Patients who complete 12 months of protocol treatment will be taken off protocol with management as per PI discretion and standards of care but will continue to be followed for progression, if the patient did not progress on study treatment, and survival.

STUDY OVERVIEW DIAGRAM

SCHEDULE OF EVENTS

Assessment	Screening ²	Cycles 1-12				EOT	Long-term follow-up
		1	8	15	22		
Day	-42 to -1						
Informed Consent+♥	X						
Medical History / Treatment History ¹	X						
Skeletal Survey	X						
ECG ³	X					X	
Physical Exam / ECOG ^{4,5}	X	X				X	
Vital Signs ⁶	X	X				X	
Height ⁷ , Weight, BSA	X	X				X	
24-hour urine ⁸	X	X				X	
Urinalysis	X					X	
C- Reactive Protein	X						
Hematology ⁹	X	X	[X]	[X]		X	
Serum Chemistry ¹⁰	X	X	[X]	[X]		X	
Pregnancy Test ^{11, 12}	X	X				X	
Disease Assessment							X ²⁰
β2-microglobulin	X						
SPEP, UPEP ¹³	X	X		[X]		X	
BM Aspirate/biopsy, cytogenetics, FISH ¹⁴	X					X	
Quantitative Immunoglobulins	X	X		[X]		X	
SFLC	X	X		[X] ¹⁵		X	

Assessment	Screening ²	Cycles 1-12				EOT	Long-term follow-up
		1	8	15	22		
Day	-42 to -1						
Neurological Assessment ¹⁶	X	X				X	
QOL Assessment ¹⁶	X	X				X	
Correlative Samples ¹⁷	X	X				X	
Sample for MRD Analysis ^{18,∞}	X					X	
Adverse Events ¹⁹		X					
Control Arm							
Lenalidomide ^{21,22, 28}		Continuous Days 1-28			X ²⁶	X ²⁶	
Experimental Arm							
Lenalidomide ^{21,23, 28}		Continuous Days 1-21			X ²⁶	X ²⁶	
Ixazomib ²⁴		X	X	X			
Dexamethasone ²⁵		X	X	X	X		
Survival and Evaluation of Second Primary malignancies							X ²⁷

- + Documented informed consent must be obtained prior to any screening procedures but can be obtained prior to the screening window of 42 days
- ♥ Informed consent is valid for 42 days – if the patient has not been enrolled/randomized within the screening window, re-consent must be obtained prior to submitting the registration packet for review
- * Variations of ± 3 days of the scheduled visit are permitted
- ∞ Using diagnostic bone marrow samples for the Adaptive ID (calibration) testing is preferred as these will have the highest disease burden. If the calibration is successful, please submit the screening bone marrow samples to determine MRD status prior to study entry. If DNA identification from the diagnostic sample fails, procure additional slides from the screening marrow as these can be used for both calibration and MRD tracking. Contact the UC Multi-Site Coordinator prior to submitting additional samples, if the initial ID test fails.

[X] Only as clinically indicated

2) Includes neuropathy history and documentation of the CTCAE grade if peripheral neuropathy is present at baseline.

Assessment	Screening ²	Cycles 1-12				EOT	Long-term follow-up
		1	8	15	22		
Day	-42 to -1						

- 3) May be within 42 days of planned treatment start. Includes: lateral radiograph of the skull, anteroposterior and lateral views of the spine, and anteroposterior views of the pelvis, ribs, femora, and humeri. Skeletal surveys performed outside of the 42-day window may be considered for inclusion 6 or 8 weeks prior to randomization. Please contact the Lead Principal Investigator and/or/CRA on a case-by-case basis.
- 4) 12-lead ECG, including QTc interval completed on local machine.
- 5) For Day 1 of cycle 1, screening results may be used if within 7 days of treatment start.
- 6) Complete physical exam (including vital signs [systolic and diastolic blood pressure, respiration, pulse, and oral temperature], weight, calculation of body surface area [BSA] & ECOG score) required at screening & Day 1 of each cycle.
- 7) Systolic and diastolic blood pressure, pulse, respiration, temperature day 1 of each cycle, EOT visit and as clinically indicated.
- 8) Height required at screening only
- 9) 24 hour urine total protein, urine protein electrophoresis (UPEP), and urine protein immunofixation. For subjects whose disease is being monitored through UPEP, additional post baseline 24-hour urine collections are required as indicated
- 10) On day 1 of each cycle and EOT visit is required, and as clinically indicated at other time-points. Hemoglobin, WBC with complete differential, platelet count, absolute lymphocyte and absolute neutrophil counts. Results must be reviewed before dosing.
- 11) On day 1 of each cycle and EOT visit is required, and as clinically indicated at other time-points. Full serum chemistry panel at screening, day 1 of each cycle and at EOT visit: sodium, potassium, chloride, bicarbonate, BUN, creatinine, glucose, total protein, albumin, calcium, total bilirubin, alkaline phosphatase, ALT, AST, LDH, and CRP. Abbreviated serum chemistry panel should be included as necessary.
- 12) Pregnancy tests for females of childbearing potential. A female of childbearing potential (FCBP) is a sexually mature female who: 1) has not had a hysterectomy or bilateral oophorectomy; or 2) has not been naturally post-menopausal for at least 24 consecutive months (i.e., menses within the preceding 24 months) See Appendix F of protocol for details.
- 13) Pregnancy tests must occur within 10-14 days and again within 24 hours prior to prescribing lenalidomide (prescriptions must be filled within 7 days. FCBP with regular or no menstruation must have a pregnancy test weekly for the first 28 days and then every 28 days while on therapy (including breaks in therapy); at discontinuation of lenalidomide and at Day 28 post the last dose of lenalidomide. Females with irregular menstruation must have a pregnancy test weekly for the first 28 days and then every 14 days while on therapy (including breaks in therapy), at discontinuation of lenalidomide and at Day 14 and Day 28 post the last dose of lenalidomide (see Appendix 13.6).
- 14) Serum protein electrophoresis and urine protein electrophoresis (the latter only for those whose disease is being followed by UPEP). Subjects with baseline urine protein greater than 200 mg/24 hours must have a UPEP to confirm VGPR or better. Obtain blood for M-protein levels measured by SPEP or quantitative immunoglobulins for those subjects in whom SPEP/UPEP are felt to be unreliable (IgA type multiple myeloma), depending upon which studies were positive at baseline. Response will be assessed comparing day 1 of each cycle values to the respective baseline (pre-induction treatment) values for each subject.

Assessment	Screening ²	Cycles 1-12				EOT	Long-term follow-up
		1	8	15	22		
Day	-42 to -1						
15) Bone marrow aspirate and biopsy – quantify % myeloma cell involvement; bone marrow sample for cytogenetics and fluorescent in situ hybridization (FISH). Please note that cytogenetic profile at the time of diagnosis will be used for patient stratification at study entry. Bone marrow aspirate and biopsy should be performed at screening, end of 12 cycles/end of treatment and at any time that a bone marrow is performed as standard of care. If CR is recorded between screening and EOT, a Bone Marrow Biopsy can be indicated as per standards of care to be performed at 6 months from randomization (with acceptable window 3-9 months; for 6 months response assessment). However, if CR is suspected within 3 months of EOT, it is acceptable to wait for the EOT BM biopsy. Repeat bone marrow biopsy/aspirate if CR is suspected and as appropriate to confirm achievement of sCR, CR, or nCR (aspirate only—biopsy not required). If institution has established flow-based multi-color study for minimal residual disease (MRD), this evaluation should include MRD evaluation. Bone marrow biopsy/aspirate performed outside of the 42-day window may be considered for inclusion. Please contact the Lead Principal Investigator and/or the CRA on a case-by-case basis.							
16) Serum Free Light Chains repeated only to confirm response.							
17) Screening and Day 1 of every cycle. Includes neurologic exam (to detect peripheral neuropathy and/or changes in pre-existing neuropathy) and examination of clinical AEs indicative of neuropathy. Collect FACT/GOG neurotoxicity questionnaire and QOL assessment at each time point above.							
18) For patients who sign additional consent: peripheral blood and bone marrow aspirate samples collected at screening, end of treatment, and any time after randomization that CR or better is suspected. Buccal mucosa swab will be collected at screening only.							
19) All patients are required to have a sample for MRD collected at screening, at the End of Treatment visit, and at any other time a Bone Marrow biopsy/aspirate is collected as SOC. Additionally, FFPE or BMA slides from diagnosis will be required for calibration of MRD by NGS for all patients. If CR is recorded between screening and EOT, a Bone Marrow Biopsy can be indicated. However, if CR is suspected within 3 months of EOT, it is acceptable to wait for the EOT BM biopsy. It is expected that samples will be collected at a minimum of two time-points for each patient. Refer to lab manual for collection and shipping instructions. Central analysis includes MRD by multi-parameter flow cytometry and MRD by gene sequencing.							
20) AEs will be collected from the time of signing informed consent to 30 days following the last dose of treatment. Please refer to section 9 for specific collection requirements.							
21) Assessment for disease progression in subjects who did not progress during treatment. At least every 3 months (+/- 30 days) for 2 years from safety follow-up visit (which must be 28days (+/- 3 days) post-last study treatment).							
22) lenalidomide must be prescribed through and in compliance with the lenalidomide REMSTM program of Celgene Corporation. Prescriptions must be filled within 7 days. Consideration should be given to prescribing lenalidomide 5 to 7 days in advance of Day 1 of each cycle to allow time for required patient and prescriber surveys, and drug shipment to patient. Any unused lenalidomide will be counted and documented by each site.							
23) Control Arm: Lenalidomide should continue at best tolerated dose of either 10 mg or 15 mg on days 1-28. If the 10 mg dose is tolerated for three cycles, it can be escalated to 15 mg per dose.							

Assessment	Screening ²	Cycles 1-12				EOT	Long-term follow-up
		1	8	15	22		
Day	-42 to -1						
24) Experimental Arm: lenalidomide dosing Days 1-21. Cycle 1-4 lenalidomide will be administered at 25 mg daily. Cycles 5-12 lenalidomide will continue at best tolerated dose days 1-21. lenalidomide should be taken in the evening at approximately the same time each day.							
25) Cycles 1-4: Ixazomib at 3-4 mg Days 1, 8, 15. Cycles 5+ Ixazomib at best tolerated dose on Days 1, 8, 15. Ixazomib should be taken on an empty stomach or at least 1 hour before or 2 hours after a meal.							

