4.3 Number of Patients

A total of 60 patients will be enrolled in a 1:1 ratio into one of two arms: IRd or lenalidomide alone. Enrollment is defined as the time of randomization. **Protocol treatment must start within 2 days of randomization.**

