5. STUDY POPULATION

5.1 Inclusion Criteria

Each patient must meet all of the following inclusion criteria to be enrolled in the study:

1. Patients who completed induction treatment followed by autologous stem cell transplant as initial therapy for symptomatic myeloma as per IMWG criteria and are considered for single agent lenalidomide maintenance or initiated single agent lenalidomide maintenance.
 - a) Patients will be eligible for enrollment in the first 0-6 months of lenalidomide maintenance provided that lenalidomide maintenance has been initiated within 6 months post transplant as per standard of care.
 - i. Patients do not have to be on Lenalidomide at the time of study consent.
 - b) Patients already in lenalidomide maintenance must be received lenalidomide 10 mg or 15 mg and be able to tolerate dose escalation to 25 mg daily.
 - c) Patients receiving off protocol lenalidomide maintenance cannot exceed 6 months post-transplant
 - d) A one week break from off protocol lenalidomide is suggested, prior to initiating treatment on the study
 - i. Any delays >7 days to align treatment with the start of Cycle 1 Day 1, of either arm, must be discussed with the PI.

- e) Patients who completed tandem transplantation will be eligible for enrollment
2. No evidence of progressive disease on lenalidomide
3. Evidence of minimal residual disease at the time of screening defined as at least MRD-positive disease.
 - a) The primary method of evaluation of MRD is Multi-parameter Flow Cytometry (MFC) performed at the University of Chicago.
 - b) Patients who have negative MRD by Multi-Parameter Flow Cytometry (MFC) but have residual original monoclonal protein by serum or urine immunofixation may be eligible if they are found to have MRD-positive disease by Next Generation Sequencing (NGS)
 - c) If patient is receiving lenalidomide, any delays required to align treatment with the start of Cycle 1 of either arm, must be discussed with the PI.
4. Bone marrow specimen from diagnosis (or pre-induction) will be required at study entry; available DNA sample will be used for calibration step for MRD evaluation by gene sequencing
5. Males and females ≥ 18 years of age
6. Life expectancy of more than 3 months
7. ECOG performance status of 0-2
8. Adequate hepatic function, with bilirubin $\leq 1.5 \times$ ULN and aspartate aminotransferase (AST) and alanine aminotransferase (ALT) $\leq 3 \times$ ULN

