8.1.1 Determination of Sample Size

A total of 60 patients (30 per arm) is based on the assumption that the rate of MRD negative disease that is approximately 20% higher in the experimental arm vs. the control arm will be considered promising for further evaluation. Because this is a proof of concept phase II randomized trial rather than a confirmatory trial, the comparison will be made using a one-sided test at 80 % power and at most 10% type I error. Table 8.1 below shows the detectable difference depending on the control rate. Boldfaced figures are values assumed most likely based on the literature and previous studies. Calculations are based on a Cochran-Mantel-Haenszel test with continuity correction.

Table 8-1 Detectable increases in the rate of MRD with 80 %power (one-sided $\alpha=0.10$)

Control Arm	Experimental Arm	Difference
2.5%	21.8 %	19.3 %
5.0%	26.7 %	21.7 %
10.0%	35.5 %	25.5%
15.0%	42.4%	27.4%
20.0%	48.1 %	28.1 %

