8.1.3.2 MRD Evaluations by gene sequencing

8.1.4As part of an additional MRD evaluation, all bone marrow aspirates collected for MRD analysis will also be analyzed using the. Clono SEQ® platform. The collection time points will be as described above: at the time of enrollment, at any time during a suspected CR or better, and at 12 months/end of treatment. The samples will be part of the same aspirate collected for multiparameter flow cytometry and the details of this collection will be described in a separate manual. All samples will be sent to the University of Chicago Multiple Myeloma Program Coordinator. Processing of samples including DNA isolation, storage, and shipment to Adaptive Biotechnologies will be performed by the University of Chicago laboratory. Samples processing at the University of Chicago will be supported by separate grants and funds from the University of Chicago investigators. Adaptive Biotechnologies will provide funding for Clono SEQ® analysis. **Populations for Analysis**

The Intent-to Treat (ITT) population of patients will be defined as all patients who receive at least one dose of treatment in either of the arms (ixazomib or lenalidomide or dexamethasone in the experimental arm or lenalidomide in the control arm). “A secondary, evaluable population will also be analyzed that will include all patients in the ITT population with the following exceptions:

- (1) Patients who discontinued the trial for reasons other than toxicity or progressive disease, and
- (2) Patients who met eligibility for MRD positive disease but the MRD testing at the 12-month timepoint is either not successful (by NGS) or the sample is not available (pt withdraws consent, sample is a dry tap, etc).

Patients in categories (1) or (2) will be rendered “non-evaluable.” Additionally, in the situation that a patient is rendered non-evaluable, a new patient will be randomized into the trial to preserve the sample size for primary endpoint analysis. Additionally, in the situation that a

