patient is rendered non-evaluable, a new patient will be randomized into the trial to preserve the sample size for primary endpoint analysis. Patients enrolled in this trial will be patients who completed initial induction followed by autologous stem cell transplant for symptomatic myeloma (per IMWG criteria) and in the first 0-6 months of Lenalidomide maintenance provided that was initiated within 6 months after transplant as per standard of care and with at least MRD-positive residual myeloma. The study's primary endpoint, attainment of MRD-negative disease by MFC will be assessed at the completion of the 12 cycle of protocol treatment (both arms). In patients that were enrolled based on their MRD-positivity by MFC, an improvement will be counted when these patients switch to MRD-negative disease by MFC at the 12-month time-point. Patients that were enrolled per their MRD-positivity by NGS will require NGS analysis to determine their MRD status at 12 months of treatment. In this patient population, only a switch from MRD-positivity to negativity by NGS will be counted as an improvement. We anticipate that no more than 10% of patients will be enrolled who are MFC negative but NGS positive. If there is an imbalance between the two treatment arms in this variable we will adjust by post-hoc stratification or covariate analysis. All patients enrolled and receiving any IRD or R treatment will be evaluable for this endpoint, with the exception of patients that decline to receive treatment for reasons unrelated to toxicity and/or efficacy. Patients in that category will be replaced. All other patients who discontinue treatment before receiving 12 cycles of protocol treatment will be considered treatment failures for assessment of the study's primary endpoint. The proportion of MRD-negative patients will be reported along with 95% confidence intervals.

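### Section 8.1.4 makes a patient non-evaluable, and replaced, when 12-month NGS fails, without limiting this to patients enrolled on NGS, although most patients' endpoint is flow

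*Combined protocol and SAP*

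**What the plan says.** **Endpoint.** Sections 2.1, 3.1 and 8.1.4 define success by entry route. A patient who entered MRD-positive by flow (MFC) must become negative by MFC. A patient who entered MFC-negative but NGS-positive must become negative by NGS. On the mix, section 8.1.4 says: "We anticipate that no more than 10% of patients will be enrolled who are MFC negative but NGS positive".

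**NGS in parallel.** Section 8.1.3.2 has every MRD aspirate sequenced as well. Section 2.3 lists NGS in parallel with MFC as exploratory.

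**Evaluability, first statement.** Section 8.1.4, whose heading runs into the end of 8.1.3.2, defines an ITT population of all treated patients and a secondary evaluable population. Item (2) removes from the evaluable population any patient who was eligible as MRD-positive but for whom "the MRD testing at the 12-month timepoint is either not successful (by NGS) or the sample is not available". Each non-evaluable patient leads to a new randomisation, to protect the sample size for the primary endpoint.

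**Evaluability, second statement.** Later in section 8.1.4, every treated patient is evaluable for the primary endpoint except those who decline treatment for reasons unrelated to toxicity or efficacy. Those patients are replaced, and other early discontinuers count as failures.

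**Calibration.** Criterion 4 of section 5.1 states: "Bone marrow specimen from diagnosis (or pre-induction) will be required at study entry". Schedule of Events footnote 19 agrees: "FFPE or BMA slides from diagnosis will be required for calibration of MRD by NGS for all patients". The schedule's infinity-symbol footnote adds a fallback: if identification from the diagnostic sample fails, sites should "procure additional slides from the screening marrow as these can be used for both calibration and MRD tracking". It makes no exception for MFC-negative patients, whose eligibility under criterion 3b depends on NGS.

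**The concern.** Item (2) names only NGS and applies to anyone who was eligible as MRD-positive. For a flow-entered patient the NGS result plays no part in the endpoint. Taken at its word, the item still drops that patient from the evaluable set, and randomises another, when the exploratory assay fails and the flow result is perfectly good. The later sentence in the same section would keep that patient. Two analysts following section 8.1.4 could therefore reach different evaluable denominators and different numbers of replacements.

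The calibration fallback raises a smaller question. NGS entry normally takes two steps: identify the clone at diagnosis, then look for it at screening. If one screening marrow serves both steps, the second adds no independent information, and these are the patients whose eligibility turns on it.

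**Working it through.** **Inputs from the documents**
- 60 patients: "A total of 60 patients will be enrolled in a 1:1 ratio into one of two arms" (section 4.3).
- Error rates: "the comparison will be made using a one-sided test at 80 % power and at most 10% type I error" (section 8.1.1).
- Assumed MRD-negative rates of 5% (control) and 26.7% (experimental) (section 8.1, Table 8-1).
- NGS-entered share of at most 10% (section 8.1.4).

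**Assumption.** The documents give no 12-month NGS failure rate, *f*. I use 5%, 10% and 20%, equal for both entry routes.

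**Step 1: the plan's own figure.** The exact power of a one-sided Fisher test at 0.10 with 30 per arm is the sum of Bin(x; 30, pC) × Bin(y; 30, pE) over all rejecting pairs (x, y). For the five rows of Table 8-1 this gives 79.9%, 80.0%, 80.1%, 80.1% and 80.0%. The stated 80% reproduces and is not in dispute.

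**Step 2: entry mix at the 10% ceiling.** NGS-entered: 60 × 0.10 = 6. Flow-entered: 60 − 6 = 54.

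**Step 3: patients removed, and randomisations needed for 60 evaluable** (rounded up, ignoring all other losses)

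| *f* | Flow-entered removed, 54*f* | NGS-entered removed, 6*f* | Randomised as written, 60/(1−*f*) | Randomised if tied to entry assay, 60/(1−0.1*f*) |
|---|---|---|---|---|
| 5% | 2.7 | 0.3 | 64 | 61 |
| 10% | 5.4 | 0.6 | 67 | 61 |
| 20% | 10.8 | 1.2 | 75 | 62 |

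The 54*f* column is an upper bound at this entry mix. It assumes that all 54 reach 12-month sampling and that every failed NGS comes with a readable flow result. Early discontinuers are already failures under section 8.1.4, and both assays use the same aspirate, so a poor sample may defeat both.

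**Step 4: if removed patients were not replaced.** At *f* = 10%, 60 × 0.90 = 54 remain (27 per arm) and exact Fisher power at 5% versus 26.7% is 75.4%. At 20%, 48 remain (24 per arm) and power is 70.0%. With the clause tied to the entry assay, 59.4 or 58.8 remain. Rounding down to 29 per arm gives 78.6%. The plan does replace, so its practical cost is the extra randomisations in Step 3.

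**Step 5: the two statements side by side.** Take a treated flow-entered patient who completes 12 cycles, has a valid MFC result and has a failed NGS. Item (2) read literally makes the patient non-evaluable and replaced. The later sentence makes the patient evaluable, scored by MFC and not replaced. Both cannot apply.

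**Step 6: calibration.** If the tracked sequence is taken from the screening marrow, it is present in that marrow. Given successful calibration, the screening result is positive. Calibration may still fail, in which case there is no NGS-positive result. At most about 6 patients enter by this route, and only those whose diagnostic identification failed would be concerned.

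**The case against.** **Item (2) can be read by entry route.** The endpoint text is specific to entry route throughout, and section 8.1.4 says NGS-entered patients are the ones who need NGS at 12 months. The clause may simply mean the test that defines that patient's endpoint. This is a fair reading and probably the intended one, but the words do not say it.

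**ITT is untouched.** This stands. A reader might infer that known flow outcomes vanish from the trial. They do not: item (2) shapes the secondary evaluable population. It still drives replacement, which the plan justifies by the primary endpoint's sample size.

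**Stronger readings that the documents do not support**
- *NGS-positive entry becomes automatic.* Calibration on a flow-negative marrow can fail, and criterion 3b also requires residual original M-protein by immunofixation.
- *An unrelated sequence would be tracked and its loss scored as success.* How the assay selects a sequence is not described.
- *The fallback cancels criterion 4.* It opens only after the required diagnostic sample has been tried, and the coordinator must be contacted before additional samples are submitted.
- *A flow-entered patient whose first calibration fails is non-evaluable from the outset.* The fallback exists for that case.
- *An unreadable flow sample has no category.* The open-ended list of unavailable samples in item (2) may cover it.
- *Replacements could be chosen after the flow result is known.* The trial is open-label, but nothing links the exclusion decision to the flow result.

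**Conclusion.** The point holds as a wording defect in item (2) of section 8.1.4 and a conflict with the later evaluability sentence in the same section. Followed literally, a failed exploratory NGS takes a valid flow result out of the secondary evaluable population and adds a randomised patient. With the NGS-entered share at its 10% ceiling and an assumed failure rate of 5% to 20%, at most about 3 to 11 flow-entered patients are affected. To reach 60 evaluable, 64 to 75 randomisations would be needed instead of 61 or 62. The failure rate is my assumption, so these figures show scale only.

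It would be wrong to conclude that the plan's NGS rules in general ignore entry route. The objectives, endpoint and scoring rules respect it; only item (2) and the calibration footnote do not. The calibration gap is real but minor: few patients could be concerned, and all of them must also be immunofixation-positive.

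**What to change.** 1. In item (2) of section 8.1.4, replace *not successful (by NGS)* with *not successful by the assay (MFC or NGS) on which the patient was enrolled*.
2. Reconcile item (2) and the replacement sentence with the later statement that all treated patients are evaluable, so that section 8.1.4 gives one list of who is evaluable and who is replaced.
3. As a minor addition, state in the infinity-symbol footnote of the Schedule of Events that, for an MFC-negative patient, a clonotype identified only in the screening marrow does not by itself establish NGS-positive eligibility. The fallback can stay for MFC-positive patients, where NGS is exploratory.

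The cost is a few lines of text. Items 1 and 2 reduce replacements. Item 3 means that an occasional MFC-negative patient whose diagnostic calibration fails could not enrol.
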